6.4 Serious Adverse Event Reporting Procedures

SAEs will be collected and recorded throughout the study period, from the first dose of the investigational agent through 100 days after the last dose of study drug or end of the study (if thought to be related to study drug), or 30 days after the initiation of a new anticancer therapy, whichever is earlier.

All SAEs, regardless of causality to study drug and/or administration device, will be

promptly	to	the	IND	sponsor ai	nd BMS		Syndax	
reported								

within 24 hours of discovery or notification of the event.

Initial SAE information and all amendments or additions must be recorded on a Serious Adverse Event Report Form and provided to Syndax and BMS or their representative. The SAE reporting procedure is provided in **Appendix F**. If this falls on a weekend or holiday, an email notification is acceptable but must be followed by an SAE reporting form on the next business day.

After the initial SAE report, the investigator is required to proactively follow each subject and provide further information to the safety department in regards to the subject's condition. All SAE(s) will be followed until:

- Resolution
- The condition stabilizes
- The event is otherwise explained
- The subject is lost to follow-up
- Death

As soon as relevant information is available, a follow-up SAE report will be submitted to the IND Sponsor, BMS, and Syndax.

For all deaths, available autopsy reports and relevant medical reports should be provided to the IND Sponsor, Syndax and BMS or their representative. If a patient is permanently withdrawn from the study because of an SAE, this information must be included in the initial or follow-up Serious Adverse Event Report Form as well as the EOT eCRF.

The Investigator should notify the IRB or EC of SAEs occurring at the site and other AE reports received from Syndax and BMS, in accordance with local procedures and statutes.

6.5 Pregnancy and Lactation Reporting Procedures

Although pregnancy and lactation are not considered AEs, it is the responsibility of Investigators or their designees to report any pregnancy or lactation in a patient (spontaneously reported to them) that occurs during the study or within 120 days of completing the study or 30 days following cessation of treatment if the patient initiates new anticancer therapy, whichever is earlier. All patients who become pregnant must be followed to the completion/termination of the pregnancy.

Pregnancy outcomes of spontaneous abortion, missed abortion, benign hydatidiform mole, blighted ovum, fetal death, intrauterine death, miscarriage, and stillbirth must be reported as SAEs (Important Medical Events). If the pregnancy continues to term, the outcome (health of infant) must also be reported.

Such events must be reported within 24 hours to the Sponsor either by electronic media or paper.

6.6 Reporting of Overdose to the Sponsor

6.6.1 Entinostat Overdose

No information on the treatment of overdose of entinostat is currently available. Entinostat overdoses are defined as a single dose greater than 15 mg. This overdose will not be considered an SAE unless the outcome of the overdose meets seriousness criteria as defined in **Section 6.2.4** In the event of an entinostat overdose, the Sponsor should be immediately notified. The patient should be carefully monitored for potential adverse reactions and symptomatic treatment instituted as per institutional standards of care.

6.6.2 Nivolumab Overdose

A nivolumab overdose is considered an SAE. No specific information is available on the treatment of overdose of nivolumab. In the event of overdose, the patient should be observed closely for signs of toxicity. Appropriate supportive treatment should be provided if clinically indicated.

6.7 Follow-Up of Adverse Events

The Investigator must continue to follow all SAEs and non-serious AEs considered to be reasonably or possibly related to study drug either until resolution or the Investigator assesses them as chronic or stable. This follow-up may extend after the end of the study.

6.8 Reconciliation of SAEs

The Principal Investigator (or designee) will reconcile the clinical database SAE cases (case level only) transmitted to the IND sponsor and BMS Global Pharmacovigilance

6.9 Safety Reporting to Health Authorities, Ethics Committees/Institutional Review Boards and Investigators

The Sponsor will send appropriate safety notifications to Health Authorities in accordance with applicable laws and regulations.

The Investigator must comply with any applicable site-specific institutional requirements related to the reporting of SAEs involving his/her patients to the EC/IRB that approved the trial.

In accordance with local regulations, the IND Sponsor or designee will notify investigators of all SAEs that are unexpected (i.e., not previously described in the IB), and related to the study drugs. This notification will be in the form of an expedited safety report (ESR) that is to be faxed to the investigators and the study coordinators. Upon receiving such notices, the investigator must review and retain the notice with the IB and where required by local regulations, the investigator will

submit the ESR to the appropriate IRB. The investigator and IRB will determine if the informed consent requires revision. The investigator should also comply with the IRB procedures for reporting any other safety information.

6.10 Food and Drug Administration (FDA) Reporting

All reporting to the FDA will be completed by the IND Sponsor.

7 Calendar-Day Telephone or Fax Report:

The IND Sponsor is required to notify the FDA of any fatal or life-threatening adverse event that is unexpected and assessed by the investigator to be possibly related to the investigational agent. Such reports are to be telephoned or faxed [contact]) to the FDA within 7 calendar days of first learning of the event. Follow-up information will be submitted to the FDA as soon as relevant information is available.

10 Calendar-Day Written Report:

The IND Sponsor is required to notify the FDA of any SAE that is unexpected and related to the investigational agent in a written IND Safety Report.

Written IND Safety Reports should include an Analysis of Similar Events in accordance with regulation 21 CFR § 312.32. All safety reports previously filed with the IND concerning similar events should be included in the analysis. The new report should contain comments on the significance of the new event in light of the previous, similar reports.

Follow-up information will be submitted to the FDA as soon as relevant information is available.

IND Annual Reports:

In accordance with the regulation 21 CFR § 312.33, the IND Sponsor shall within 60 days of the anniversary date that the IND went into effect submit a brief report of the adverse events and progress of the investigation. Please refer to Code of Federal Regulations, 21 CFR § 312.33 for a

list of the elements required for the annual report. All IND annual reports will be submitted to the FDA by the IND Sponsor.

6.11 Protocol Deviations Due to an Emergency or Adverse Event

Departures from the protocol will be determined as allowable on a case-by-case basis and only in the event of an emergency. The Investigator or other physician in attendance in such an emergency must contact the PI as soon as possible to discuss the circumstances of the emergency.

The PI in conjunction with the Investigators, will decide whether the patient should continue to participate in the study. All protocol deviations and reasons for such deviations must be noted on the eCRF.

6.12 Safety Monitoring

The safety and tolerability of the investigational treatments will be monitored throughout the course of the study by the Investigators and the Sponsor Study Physicians(s).

The safety and tolerability data that will be reviewed will include, but are not limited to: AEs, unacceptable toxicities, laboratory test results, and patient discontinuations. Additionally, the development of SAEs will be assessed by the IND Sponsor Study Physician(s) on a continuous basis. (**NOTE**: all SAEs must be reported to the IND Sponsor, Syndax and BMS or designee within 24 hours of discovery or notification of the event [**Section 6.4**].)

No formal safety stopping rules are specified in the protocol. However, if any significant safety issues arise, a decision to modify or terminate the study will be made by the Sponsor in collaboration with the Investigators.

[figure not shown]
7. PHARMACEUTICAL INFORMATION

A list of the adverse events and potential risks associated with the investigational agents administered in this study can be found in **Section 6.1**. Additional drug information can be found in the investigational agent's Investigator Brochure.

	_		

7.2 Nivolumab (NSC #748726)

	J		

_

8. MEASUREMENT OF EFFECT

8.1 Antitumor Effect – Solid Tumors (RECIST 1.1)

Although the clinical benefit of these drugs has not yet been established, the intent of offering this treatment is to provide a possible therapeutic benefit, and thus the subjects will be carefully monitored for tumor response and symptom relief in addition to safety and tolerability. Subjects will be assessed by standard criteria for response per the timelines noted in the Study Calendar (Section 10).

Response and progression will be evaluated in this study using the new international criteria proposed by the revised Response Evaluation Criteria in Solid Tumors (RECIST) guideline (version 1.1) [123]. Changes in the largest diameter (unidimensional measurement) of the tumor lesions and the shortest diameter in the case of malignant lymph nodes are used in the RECIST criteria.

In addition, if a formal reading for RECIST measurements is performed, but the results are not available prior to the scheduled start of the next cycle, treatment should continue based upon review of the routine/clinical radiologist report of the status of disease (e.g., response, stability or progression). In the event that a RECIST re-read would have changed the treatment decision for the subject, if known prior, the IND Sponsor/designee should be consulted and course of action

clearly documented in the medical record. If it is in the best interests of the subject to continue on study, this is permissible. These cases will be reviewed in detail at the time of study analyses.

8.2 Definitions

Evaluable for toxicity: All patients will be included in the toxicity summaries, from the time of their first treatment with study drug.

Evaluable for objective response: All patients must be accounted for in the summary of objective response. To formally classify a patient as RECIST-evaluable, only those patients who have measurable disease present at baseline (one of the eligibility criteria, **Section 3.1**) and start treatment (received at least one dose of entinostat) will be considered evaluable. These patients will have their response classified according to the definitions stated below (**NOTE**: Subjects who exhibit objective disease progression prior to the end of cycle 1 will also be considered evaluable.)

8.2.1 Disease Parameters

Measurable disease: Measurable lesions are defined as those that can be accurately measured in

be recorded in millimeters (or decimal fractions of centimeters).

NOTE: Tumor lesions that are situated in a previously irradiated area might or might not be considered measurable. In most cases, in the event of post-radiation disease progression, previously irradiated lesions may be considered measurable lesions. Otherwise, these lesions should be considered non-measurable.

Malignant lymph nodes: To be considered pathologically enlarged and measurable, a lymph node must be $\geq 15 \text{ mm}$ ($\geq 1.5 \text{ cm}$) in short axis when assessed by CT scan (CT scan slice thickness recommended to be no greater than 5 mm [0.5 cm]). At baseline and in follow-up, only the short axis will be measured and followed.

Non-measurable disease: All other lesions (or sites of disease), including small lesions (longest

axis), are considered non-measurable disease. Bone lesions, leptomeningeal disease, ascites, pleural/pericardial effusions, lymphangitis cutis/pulmonitis, inflammatory breast disease, and abdominal masses (not followed by CT or MRI), are considered as non-measurable.

NOTE: Cystic lesions that meet the criteria for radiographically defined simple cysts should not be considered as malignant lesions (neither measurable nor non-measurable) since they are, by definition, simple cysts.

'Cystic lesions' thought to represent cystic metastases can be considered as measurable lesions, if they meet the definition of measurability described above. However, if non-cystic lesions are present in the same subject, these are preferred for selection as target lesions.

Target lesions: All measurable lesions up to a maximum of 2 lesions per organ and 5 lesions in total, representative of all involved organs, should be identified as target lesions and recorded and measured at baseline. Target lesions should be selected on the basis of their size (lesions with the longest diameter), be representative of all involved organs, but in addition should be those that lend themselves to reproducible repeated measurements. It may be the case that, on occasion, the largest lesion does not lend itself to reproducible measurement in which circumstance the next largest lesion which can be measured reproducibly should be selected. A sum of the diameters (longest for non-nodal lesions, short axis for nodal lesions) for all target lesions will be calculated and reported as the baseline sum diameters. If lymph nodes are to be included in the sum, then only the short axis is added into the sum. A sum of the longest diameter (LD) for all target lesions will be used as reference by which to characterize the objective tumor response.

Non-target lesions: All other lesions (or sites of disease) including any measurable lesions over and above the 5 target lesions should be identified as non-target lesions and should also be recorded at baseline. Measurements of these lesions are not required, but the presence, absence, or in rare cases unequivocal progression of each should be noted throughout follow-up.

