3. PATIENT SELECTION

3.1 Eligibility Criteria

- **3.1.1.** Patients must have histologically or cytologically confirmed cholangiocarcinoma or pancreatic adenocarcinoma that is metastatic or unresectable and has progressed despite standard therapy or is intolerant of therapy; 1 or 2 prior chemotherapy regimens in the metastatic setting or progression < 6 months from the completion of adjuvant chemotherapy.
- **3.1.2.** Age ≥18 years.
- **3.1.3.** ECOG performance status of 0 or 1 (Karnofsky \geq 70%, see Appendix A).
- **3.1.4.** Life expectancy of greater than 12 weeks.
- **3.1.5.** Patients must have normal organ and marrow function as defined below:
 - Hemoglobin (HgB) $\geq 9.0 \text{ g/dL}$
 - Leukocytes \geq 3,000/mcL
 - Absolute neutrophil count $\geq 1,500/mcL$
 - Platelets $\geq 100,000/mcL$
 - Total bilirubin ≤ 1.5 x institutional upper limit of normal (ULN); an exception to this may be allowed for participants with Gilbert's syndrome with documented approval by the Protocol Chair
 - AST(SGOT)/ALT (SGPT) $\leq 3 \times$ institutional ULN
 - Creatinine within normal institutional limits

or

• Creatinine clearance ≥ 60 mL/min using the Modified Cockcroft-Gault, as the formula below:

Female CrCl = (140 - age in years) x weight in kg x 0.85

72 x serum creatinine in mg/dL

Male CrCl = (140 - age in years) x weight in kg x 1.00

72 x serum creatinine in mg/dL

- **3.1.6.** Negative *(serum or urine)* pregnancy test, for women of childbearing potential. NOTE: If a patient has a positive or indeterminate serum or urine pregnancy test, then an ultrasound must be done to rule out pregnancy to enroll on trial. A serum B-HCG value of <25 is considered a negative pregnancy test.
- **3.1.7.** Patients must have measurable disease per RECIST 1.1. (see Section 8.1)
- **3.1.8.** Patient must have an accessible non-bone tumor lesion from which serial core biopsy specimens can be obtained.

NOTE: Patients with bone only disease are not eligible due to difficulties in obtaining serial bone biopsies for correlative analyses.

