8.2.2 Methods for Evaluation of Measurable Disease

All measurements should be taken and recorded in metric notation using a ruler or calipers. All baseline evaluations should be performed as closely as possible to the beginning of treatment and

never more than 28 days before the beginning of the treatment. Tumor response will be assessed per RECIST 1.1 using radiographic scans every 8 weeks±7 days.

The same method of assessment and the same technique should be used to characterize each identified and reported lesion at baseline and during follow-up. Imaging-based evaluation is preferred to evaluation by clinical examination unless the lesion(s) being followed cannot be imaged but are assessable by clinical exam.

Clinical lesions: Clinical lesions will only be considered measurable when they are superficial

calipers (e.g., skin nodules). In the case of skin lesions, documentation by color photography, including a ruler to estimate the size of the lesion, is recommended.

Chest x-ray: Lesions on chest x-ray are acceptable as measurable lesions when they are clearly defined and surrounded by aerated lung. However, CT is preferable.

Conventional CT and MRI: This guideline has defined measurability of lesions on CT scan based on the assumption that CT slice thickness is 5 mm (0.5 cm) or less. If CT scans have slice thickness greater than 5 mm (0.5 cm), the minimum size for a measurable lesion should be twice the slice thickness. MRI is also acceptable in certain situations (e.g., for body scans).

MRI has excellent contrast, spatial, and temporal resolution; however, there are many image acquisition variables involved in MRI, which greatly impact image quality, lesion conspicuity, and measurement. As with CT, if an MRI is performed, the technical specifications of the scanning sequences used should be optimized for the evaluation of the type and site of disease. Furthermore, as with CT, the modality used at follow-up should be the same as was used at baseline and the lesions should be measured/assessed on the same pulse sequence.

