9.2 Collection of Specimens

9.2.1 Tissue Samples

Mandatory and optional tumor biopsies will be obtained at the time points as outlined above and on the Study Calendar.

Subjects will undergo a direct or image-guided research biopsy procedure. FNA and on-site cytopathologic evaluation, where appropriate, will be done for sample/site adequacy followed by

core biopsies for collection of tissue for the research correlates outlined. The biopsy site will be clearly documented in the records; baseline and each follow-up biopsy will preferentially be done in the same organ site.

Approximately six (6) core biopsy specimens will be obtained with each biopsy as outlined; the cytopathology slide will also be retained and submitted, if performed. Up to three cores will be placed in formalin solution and paraffin embedded. The remaining biopsy specimens will be flash frozen in liquid nitrogen and then stored as fresh tissue at \leq -70°C for extraction of DNA and RNA. The biopsy specimens will be stored and batch shipped at the latest at the conclusion of study enrollment.

The study staff will be notified when a biopsy is taking place. If core biopsy is not possible, other methods may be approved in advance by the IND Sponsor/designee.

If a subject discontinues the study prior to a planned follow-up biopsy, an attempt should be made to collect the next scheduled biopsy when the decision is made to discontinue and prior to initiation of additional treatment, if possible.

In the event that a subject cannot undergo a second biopsy for any reason, including refusal, or the baseline biopsy was unsuccessful or invaluable, the second and the third biopsies, as well as the optional biopsy at the time of progression, will not be required and the subject will continue to be treated per study protocol.

NOTE: Archival tumor specimens from previously collected samples will be obtained for correlative analysis, if available.

Biopsy Instructions

Acceptable biopsy sites are:

- Percutaneous biopsy of deep sites with local anesthetic and/or sedation (with an expected risk of severe complications < 2%)
- Cutaneous biopsy of palpable sites with local anesthetic and/or sedation with an expected risk of severe complications < 2%
- No open surgical or laparoscopic procedures will be performed solely to obtain a biopsy for this protocol.

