NOTE: If applicable, the daily dose of entinostat may occur prior to hematology/chemistry tests and these laboratory tests may be drawn at the same time as the correlative blood samples.

- ^{19.} A third mandatory biopsy will be performed at week 6 from Cycle 1, Day1. A window of +14 days applies to this time point
- ^{20.} An optional biopsy will be performed at the time of disease progression.
- ^{21.} Archival tumor specimens from previously collected samples will be obtained for correlative analysis, if available.
- ^{22.} Weekly assessments for toxicity/adverse events may occur by phone on days when entinostat alone is administered. Additionally, assessments are to continue for 30 days after the last dose of nivolumab (at intervals <21 days) or to resolution of drug-related AEs to \leq Grade 1, whichever occurs later. SAEs that occur within 100 days of the last treatment or before initiation of a new antineoplastic treatment should also be followed and recorded. These may occur by phone for subjects no longer being seen at the institution; however, an in-person clinic visit may be needed to confirm event resolution and/or to effectively evaluate possible immune-related events. Subjects must be told of follow-up requirements at study entry.
- ^{23.} Subjects who complete or discontinue from treatment because of progression disease will be followed (by phone or email) every three months (+/- 2 weeks) after completion of the EOT visit for up to 2 years or study closure to monitor overall survival. Information of other cancer therapies after discontinuation from the study treatment will also be collected.

For subjects who discontinue treatment for reasons other than tumor progression, will be contacted (by phone or email) every three months (+/- 2 weeks) after completion of the EOT for up to 2 years or study closure to monitor overall survival, and information

93

about disease status will be also collected if possible (i.e. radiological imaging and/or tumor markers) until documented tumor progression.

NOTE: For evaluation of PFS, all subjects who discontinue study drug administration prior to 6 months must have restaging scans/imaging within a 7 day window of the 6 month time point from the date of initiation of combination treatment

J1798/Version 5.0/May 21, 2020

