12.2 Sample Size and Accrual Rate

Approximately 27 patients with unresectable or metastatic CCA and 27 patients with locally advanced or metastatic PDAC will be enrolled, with ORR as the primary endpoint. Enrollment will be carried out in 2 stages so that the study can terminate early if the combination of entinostat plus nivolumab is not sufficiently effective.

Simon's two-stage, minimax, design will be employed in each cohort to test the null hypothesis that the true ORR is 5% or less (not considered clinically compelling for this combination). In the first stage, 13 subjects will be accrued.

If there are no responders among the first 13 subjects, the study will be terminated for futility. Otherwise, 14 additional subjects will be accrued to target a total of 27 treated and response evaluable subjects. The null hypothesis will be rejected if 4 or more responses are observed in 27 subjects per each cohort.

The probability of stopping the trial early for futility is 51% if the true ORR is 5% or less. This design yields 80% power at a one-sided type I error rate of 5% when the true response rate is 20% The study may enroll 33 subjects per cohort to ensure 27 would be evaluable for the primary efficacy endpoint. We expect to enroll 4-6 patients per month. We estimate that we could reach the accrual goal within 1 year.

Any patient who comes off of study due to toxicity before completing the first cycle of treatment, without evidence of disease progression may be replaced.

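### Nothing keeps a serially biopsied lesion out of the RECIST target sum, so swelling after the third biopsy can mask a response or mimic progression at the first scan

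*Combined protocol and SAP*

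**What the plan says.** - **Target lesions (8.2.1).** All measurable lesions are targets, up to two per organ and five in total. On selection: "Target lesions should be selected on the basis of their size (lesions with the longest diameter), be representative of all involved organs". The sentence goes on to ask for lesions that can be measured reproducibly.
- **Lesion to biopsy (3.1.8).** "Patient must have an accessible non-bone tumor lesion from which serial core biopsy specimens can be obtained". Measurable disease is a separate criterion (3.1.7). The two need not be met by different lesions.
- **Biopsies (9.1, 9.2.1).** Three are mandatory: at day -14, after the entinostat lead-in, and about 6 weeks after Cycle 1 Day 1. "Approximately six (6) core biopsy specimens will be obtained with each biopsy as outlined". Repeat biopsies should preferably be in the same organ. The biopsy site is recorded, but not linked to target selection.
- **Timing (Study Calendar).** On the third biopsy, footnote 19 says: "A window of +14 days applies to this time point". Footnote 18 gives ±3 days and places the week-6 sample before Cycle 2 Day 15 dosing. On scans, 8.2.2 says: "Tumor response will be assessed per RECIST 1.1 using radiographic scans every 8 weeks±7 days". Footnote 2 counts them from Cycle 1 Day 1.
- **Comparable rule.** Previously irradiated lesions are restricted as targets (3.2.1, 8.2.1). Biopsied lesions have no such rule.
- **Decision rule (12.2).** Each cohort is to "test the null hypothesis that the true ORR is 5% or less". "If there are no responders among the first 13 subjects, the study will be terminated for futility". Four or more responses in 27 reject the null.

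**The concern.** In a patient with few lesions, the cored lesion is a target by default. Section 9.2.1 expects most biopsies to be of liver, where at most two lesions can be targets, so one altered lesion can be a large share of the sum. If a biopsy bleeds shortly before the first response scan, the measured diameter can rise for a reason unrelated to treatment.

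The effect on the primary endpoint would be one of two kinds. A true partial response may be read as stable disease. Or the sum may cross the progression threshold. Section 8.3.3 counts best response only until progression, and 4.9 dates progression at the first event even when treatment continues, so a false progression can close the window in which a later response would count. Each cohort is decided at 0 versus 1 response in 13 and at 3 versus 4 in 27, so a single altered reading could matter.

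**Working it through.** **1. The plan's own figures.** Early stopping is (1 − p)^13. P(reject) = Σ over x = 1 to 13 of P(X₁ = x) × P(X₂ ≥ 4 − x), with X₁ ~ Bin(13, p) and X₂ ~ Bin(14, p).
- p = 0.05: early stopping 0.513, type I error 0.0416.
- p = 0.20: power 0.801.

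These agree with the stated 51%, 5% limit and 80%.

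**2. Timing.** With footnote 19's window the third biopsy falls in weeks 6 to 8. The first scan falls in weeks 7 to 9. The overlap is weeks 7 to 8. The earlier biopsies are roughly 8 and 10 weeks before a week-8 scan, so the third matters most for transient swelling.

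**3. Effect on one patient.** Assume, for illustration, a 5 mm enlargement; the documents give no figure. PR needs a fall of at least 30% from baseline, and PD a rise of at least 20% and 5 mm from the smallest sum (8.3.1).
- Sole 15 mm target, unchanged by treatment: 20/15 = +33%, which is PD.
- A 5 mm rise alone reaches 20% only if the sum is 25 mm or less (5/25 = 20%).
- Sole 15 mm target in true PR at 10.5 mm: 15.5/15 = +3%, read as SD. PR is recorded only if the true sum is at most 10.5 − 5 = 5.5 mm, so true shrinkage from 30% up to 63% is masked.
- Sum of 60 mm: PR is recorded only if the true sum is at most 42 − 5 = 37 mm, so only shrinkage from 30% up to 38% is masked. The same 5 mm is +8% on an unchanged sum, so not PD.

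**4. How many patients bleed.** Section 9.2.1 cites 8 minor bleeds in 244 research biopsies, and a local liver-biopsy complication rate below 1%. Assume the same rate at each biopsy and independence over three: g = 1 − (1 − q)³.

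| Rate per biopsy, q | g | Patients of 27 | True responders among them at 20% ORR |
|---|---|---|---|
| 1% (ceiling of the local rate) | 3.0% | 0.8 | 0.16 |
| 8/244 = 3.3% | 9.5% | 2.6 | 0.51 |

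For the third biopsy alone: 27 × 0.01 = 0.3 and 27 × 8/244 = 0.9 patients.

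**5. Upper bound on lost power.** If every bleed cancelled a response, p = 0.20 × (1 − g).
- q = 1%: p = 0.194, power 0.780.
- q = 8/244: p = 0.181, power 0.728.

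**6. Can tissue removal create a PR?** A sole spherical target must lose 1 − 0.7³ = 66% of its volume. Assume all 18 cores come from one lesion, core diameter 0.6 to 1.2 mm (not in the documents), core length no longer than the lesion (maximum 20 mm), and no refilling. The diameter then falls by 3% to 15% for a 10 mm lesion, 1.5% to 6% for 15 mm and about 1% to 3% for 20 mm. None reaches 30%. With two equal targets the biopsied one would have to shrink 60%. With four or more it cannot produce a PR alone.

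**The case against.** The strongest opposing case is that the effect is rare and partly self-correcting.

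- Most minor bleeds need not change a target diameter. This stands, and it is why step 5 is only a bound.
- ORR counts a response at any time (1.4.1, 12.3.1) and scans repeat, so a masked response is often delayed, not lost. This stands for masking. It does not help after a false PD, or if the patient progresses before a later scan shows the response.
- Confirmation of response is required (8.3.4). This limits false responses but does not protect against a cancelled one. The repeat scan 4 weeks after initial PD (note to Table 8.3.1) applies when treatment continues, and 4.9 still dates progression at the first event.
- The reproducibility clause in 8.2.1 might lead a reader to avoid biopsied lesions. It does not mention them, so it helps only if applied that way.
- Under footnote 18 the third biopsy is nominally two weeks before the scan. This stands, but footnote 19 allows +14 days.
- Later biopsies are waived if one fails or is refused, and only the organ, not the lesion, is preferred for repeats. Many patients will therefore have fewer than 18 cores in one lesion.

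A reader might infer that biopsies could also manufacture responses and inflate the type I error. The documents do not support this. Baseline evaluations precede registration and biopsies follow it (footnote 1), so bleeding normally enlarges only the later measurements, and tissue removal stays below the PR threshold in step 6. Removal could at most tip a small sole target already near −30%.

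**Conclusion.** The omission is real: a lesion cored up to three times can be a target lesion, and the third biopsy can precede the first response scan by days. What follows is a low-frequency risk, mainly in patients with a small or sole target, that swelling masks or delays a PR or yields a false PD.

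The size of the bias in ORR cannot be established, because no rate of diameter change is given. Under the assumptions in step 4, about 0.8 to 2.6 of 27 patients would have any bleed. Under the extreme assumption that each bleed cancels a response, power is 78% or 73% instead of 80%.

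A reader might instead force one misclassified patient into every trial, which gives a type I error of 12.6% to 13.9% or power of 64%. Those figures show how sensitive a 27-patient design is to any reading error. They do not estimate the effect of biopsies. The point is a cheap improvement of low to moderate importance, not a flaw that undermines the design.

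**What to change.** - **Footnotes 2 and 19.** When the third biopsy and first restaging scan windows coincide, do the scan before the biopsy.
- **8.2.1 and 9.2.1.** Where more than one suitable lesion exists, prefer to biopsy one that is not a target. In the liver, a third suitable lesion is enough, because at most two can be targets.
- **eCRF and 12.3.1.** Flag every target lesion that is biopsied. Report a sensitivity ORR, with exact interval, that omits those patients. Leave the primary ORR and the 0/13 and 4/27 rules unchanged. Patients whose only measurable lesion is the biopsied one stay in the primary analysis and are identified by the flag.
- **Footnotes 18 and 19.** Reconcile the ±3 day and +14 day windows for the week-6 biopsy.

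The cost is a few sentences, one eCRF field and one extra table row, with no added scan, biopsy or reader. N, type I error and power are unchanged. The downside is a slightly narrower choice of biopsy site, or of target lesions, in some patients. The sensitivity ORR will also rest on fewer than 27 patients, so it is descriptive only.
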